### **8.7.2. Failure to Achieve Sustained Virologic Response**

Subjects may fail to achieve sustained virologic response if they meet virologic failure criteria or for other non-virologic reasons (such as premature discontinuation of study drug or lost to follow-up).

There are two types of virologic failure: on-treatment virologic failure and post-treatment relapse.

#### **8.7.2.1. On-Treatment Virologic Failure**

On-treatment virologic failure is defined as any of the following, while on-treatment:

- Not achieving  $\text{HCV RNA} < \text{LLOQ}$
- Confirmed 1  $\log_{10}$  increase in HCV RNA from post-baseline nadir (would call this “virologic rebound” if we want to name it in parenthesis)
- Confirmed increase in  $\text{HCV RNA} \geq \text{LLOQ}$  in any subject who achieved  $\text{HCV RNA} < \text{LLOQ}$

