ranging from 6 to 14 nM and 33 to 80 nM, respectively, which were 4- to 14-fold more potent than sofosbuvir. A comprehensive nonclinical development program has fully characterized the nonclinical pharmacology, pharmacokinetics and metabolism, and nonclinical toxicology of BEM. BEM has a clean nonclinical safety profile, with no target organs of toxicity identified in toxicology studies up to 13 weeks in duration, no evidence for genetic toxicity, no concerning findings in developmental and reproductive toxicology studies, and no test-article related findings in safety pharmacology studies. In the Phase 1 clinical study AT-01B-001 (N=88), healthy or HCV-infected subjects received either single or multiple doses (seven daily doses) up to 600 mg BEM (equivalent to 553 mg AT-511 free base). Rapid and potent pan-genotypic antiviral activity was observed with BEM, regardless of cirrhosis status. Mean maximum HCV RNA reductions of  $4.4 \log_{10}$  IU/mL after 7 days of dosing with BEM (553 mg free base) were observed in non-cirrhotic GT1 HCV-infected subjects. Similar potent antiviral activity was also observed in both non-cirrhotic GT3 and Child-Pugh A cirrhotic HCV-infected subjects, with mean maximum HCV RNA reductions of  $4.5 \log_{10}$  IU/mL and  $4.6 \log_{10}$  IU/mL, respectively, after 7 days of dosing with BEM (553 mg free base). Pharmacokinetic-pharmacodynamic (PK-PD) analysis indicated that antiviral activity closely correlated with plasma exposure of AT-273. Maximal effect ( $E_{max}$ ) modeling demonstrated that BEM doses of 550 mg free base will result in maximal viral load reduction. In the Phase 2 study AT-01B-002 (N=10), daily treatment with 550 mg BEM and 60 mg daclatasvir was evaluated for durations of 8 to 12 weeks. Despite the use of a less potent first-generation HCV NS5A inhibitor, viral load decreased rapidly, with 70% of subjects achieving plasma HCV RNA < lower limit of quantitation (LLOQ) by Week 2 (and 50% achieving target not detected by Week 2). Eight of the 9 subjects who received 8 weeks of treatment went on to achieve sustained virologic response at 12 weeks posttreatment (SVR12), and the single subject who received 12 weeks of treatment also achieved SVR12. The very rapid early clearance of HCV RNA observed in this study supports continued evaluation of BEM with a more potent, next-generation HCV NS5A inhibitor. In addition, this study provided proof-of-concept that a drug combination including BEM (albeit with a first-generation NS5A inhibitor) could result in SVR12 with 8 weeks of treatment. In the HCV program, BEM doses up to 550 mg daily have been well tolerated for durations up to 8-12 weeks. Adverse events (AEs) were generally mild or moderate in intensity, with no clinically relevant patterns in laboratory, electrocardiogram (ECG), or vital signs parameters. Additional details on the clinical and non-clinical studies are described in the BEM Investigator's Brochure.

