#### **8.7.2.2. Post-Treatment Relapse**

Post-Treatment Relapse is defined as  $\text{HCV RNA} \geq \text{LLOQ}$  after treatment discontinuation in a subject who completed the treatment regimen (at least 51 days) and who had  $\text{HCV RNA} < \text{LLOQ}$  at the time of treatment discontinuation.

Note: Week 8 HCV RNA should be considered “on-treatment” in any subject who received 51 or more days of treatment.

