#### 8.7.4. Primary Efficacy Analysis

The primary efficacy endpoint is the proportion of subjects in the PK and Pill compliant per-protocol population (PK/PC-PP) achieving sustained virologic response at 12 weeks post-treatment (SVR12). Table 5 will be used to derive SVR12 in the analysis populations.

**Table 5. Determination of primary outcome (SVR12) for subjects who meet all I/E criteria, did not receive prohibited medications and otherwise met population definition criteria.**

On-Treatment Experience	Has	Has	EOT or	Qualifying Result	Primary Outcome
	12W Post RNA	24W Post RNA	W4 Post HCV Positive		
Met Population Specific Criteria	Y			12W Post	12W Post Result
	N	Y		24W Post	24W Post Result
	N	N	Y	Last value	Failure
	N	N	N	NONE	Excluded from population
Early DC for Drug-Related AE	Y				12W Post Result
	N	Y			24W Post Result
	N	N	Y		Failure
	N	N	N		Failure
Early DC for Virologic Failure			Y		Failure
Other					Excluded from population

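### If SAP 8.7.2.1 is applied, its never-below-LLOQ criterion has no timepoint or minimum exposure, so early non-virologic stoppers can be counted as virologic failures

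*SAP*

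**What the plan says.** SAP 8.7.2 divides failure to achieve SVR into virologic failure and "other non-virologic reasons (such as premature discontinuation of study drug or lost to follow-up". Virologic failure has two types.

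- **On-treatment failure (SAP 8.7.2.1).** "On-treatment virologic failure is defined as any of the following, while on-treatment": not reaching HCV RNA below LLOQ, a confirmed 1 log10 rise from nadir, or a confirmed return to LLOQ or above after having been below it. The second and third items need confirmation. The first has no confirmation, visit or exposure requirement.
- **Relapse (SAP 8.7.2.2).** Quantifiable RNA "after treatment discontinuation in a subject who completed the treatment regimen (at least 51 days) and who had" RNA below LLOQ at that time. A note adds that the Week 8 value counts as on-treatment "in any subject who received 51 or more days of treatment".

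Two other places define virologic failure without the first item. SAP 8.8, on the secondary endpoints, gives only the two confirmed rises. Protocol 5.6.1, the individual stopping rule, gives the same two.

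SVR12 is derived separately: "Table 5 will be used to derive SVR12 in the analysis populations". In that table a subject who meets the population criteria and has a 12-week sample takes the 12-week result. EOT or Week 4 positivity decides the outcome only when the 12-week and 24-week samples are both missing.

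**The concern.** Not being below LLOQ tells us about the drug only once the subject has had time to respond. Without a timepoint, the item mixes non-response with short exposure. A subject who stops in the second week while RNA is falling normally would be called a virologic failure by SAP 8.7.2.1 and a non-virologic one by SAP 8.7.2, and no rule says which prevails.

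Virologic failure is a secondary endpoint, analysed in EE-PP, PC-PP and PK/PC-PP and repeated in the safety population (SAP 8.7.5). It selects subjects for the emergent-RAV analysis (SAP 8.9). It also drives the lead-in gate (SAP 4.1 and 5.1). At stake are an inflated failure rate, tolerability dropouts in the resistance denominator and, less often, an extra count at the gate.

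**Working it through.** **1. Cases run through the text**

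| Subject | SAP 8.7.2.1, first item | SAP 8.8 / Protocol 5.6.1 | Where the subject is analysed |
|---|---|---|---|
| A. Stops Day 10 at own request, RNA falling but quantifiable, 12-week value available | Failure | Not a failure unless a confirmed rise is seen | EE-PP and safety; excluded from PC-PP and PK/PC-PP |
| B. Stops early for a drug-related AE, never below LLOQ | Failure | As for A | Every population whose other criteria are met, including PC-PP (gate) |
| C. Takes all 56 days, quantifiable through Week 8, below LLOQ at post-treatment Week 12 | Failure, while Table 5 gives SVR12 success | Not a failure unless a confirmed rise is seen | As for B |

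A subject who stops at Day 30 already below LLOQ and rebounds afterwards is not a relapse, because relapse applies only "in a subject who completed the treatment regimen (at least 51 days". So SAP 8.7.2 would count the early stopper who had not yet suppressed as virologic, but not the one who had suppressed and then rebounded. The missing exposure condition causes that asymmetry.

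**2. Added failures, illustrative**

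Inputs: 280 subjects (planned enrollment). Share still quantifiable at Week 2: 30%, the complement of "70% of subjects achieving plasma HCV RNA < lower limit of quantitation (LLOQ) by Week 2" in Protocol 1.1. That study had 10 subjects and a different NS5A partner; the Wilson 95% interval for 3/10 is 10.8% to 60.3%. Early non-virologic stopping of 1% to 5% at about Week 2 is an assumption; the documents give no rate.

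Formula: added failures = N × stopping rate × share still quantifiable.

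- Low: 280 × 0.01 × 0.30 = 0.84
- High: 280 × 0.05 × 0.30 = 4.2
- With the share varied from 11% to 60%: 280 × 0.01 × 0.11 = 0.31, up to 280 × 0.05 × 0.60 = 8.4

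If 8 of 280 truly fail, the rate is 2.9% (Wilson 95% CI 1.5 to 5.5). With 4 stoppers reclassified it is 12/280 = 4.3% (2.5 to 7.3).

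**3. Lead-in gate**

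The SAP figure reproduces: 6/60 = 10.0% passes and 7/60 = 11.7% closes enrollment. With an assumed true failure rate of 5% and n = 60:

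- none reclassified: P(Bin(60, 0.05) ≥ 7) = 3.0%
- one reclassified: P(Bin(59, 0.05) ≥ 6) = 7.4%
- two reclassified: P(Bin(58, 0.05) ≥ 5) = 16.4%

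These are conditional on a reclassification occurring. Even if every early stopper had a drug-related AE, the expected number is 60 × 0.01 × 0.30 = 0.18 to 60 × 0.05 × 0.30 = 0.9.

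**4. Case C in the tables**

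Take 253/266 with SVR12 (95.1%) and 13/266 true failures (4.9%), which sum to 100%. Each subject counted both ways adds 1/266 = 0.38 points.

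**The case against.** The strongest reply is that SAP 8.8 governs the secondary endpoint and leaves the item out, as does Protocol 5.6.1. If SAP 8.8 alone is programmed, the item does no harm, so a statement that early stoppers will be counted as failures goes beyond the documents. That stands, and the point is conditional for this reason. It does not settle the matter. The analysis bullet in SAP 8.8 names on-treatment failure and relapse, the two types defined in SAP 8.7.2, and the interim analysis in SAP 5.1 uses the same pair. SAP 8.7.2.1 also still carries a drafting comment.

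Second, a reader might infer that Case C is definitely both cured and failed. The item sits in a section on failure to achieve SVR, and Protocol 8.4.1 tabulates reasons only among SVR12 failures, so it can fairly be read as not reaching SVR12 successes. Nothing requires the two proportions to sum to 100%. What stands is narrower: no text excludes the double count.

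Third, a reader might infer that all early stoppers threaten the gate or the primary result. They do not. Withdrawn-consent stoppers never enter PC-PP or PK/PC-PP, and EE-PP needs a collected or imputed 12-week value unless the stop is for an AE or virologic failure. Protocol 1.2.2 calls drug-related discontinuations rare for RZR, and Protocol 1.4 calls BEM tolerability at this dose comparable to placebo.

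Finally, the 51-day note might seem to supply the missing exposure condition. It classifies the Week 8 sample only; at most it hints that an end-of-treatment judgement was intended.

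**Conclusion.** The point holds in conditional form. Where SAP 8.7.2.1 is applied, a stated rule gives a result that SAP 8.7.2 contradicts, and the plan does not say which definition is programmed. It should be corrected, but it does not touch the primary SVR12 rate.

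The size is illustrative: about 1 to 4 added failures of 280, or 0.3 to 8.4 over the uncertainty of the 10-subject study. It rests on assumed stopping of 1% to 5% and a proxy regimen. Because it is computed on all 280, it describes the supplemental safety population; EE-PP would see less, and PC-PP and PK/PC-PP only the drug-related-AE stoppers.

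A sharper figure is tempting. With stops uniform over Days 2 to 50 and a log-normal time to below LLOQ (median 10 days, 70% by Day 15), about 23% of early stoppers are relabelled: 3.3 of 14, moving an assumed 5.0% safety-population failure rate to about 6.2%. The documents do not support quoting that as an estimate. The stopping pattern, the median and the baseline rate are all assumed, and the 70% comes from 10 subjects.

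**What to change.** For analysis classification only:

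1. Restate the first item of SAP 8.7.2.1 as: *HCV RNA never < LLOQ through the Week 8 (last on-treatment) sample in a subject who received at least 51 days of treatment.* The threshold is the SAP's own.
2. Classify subjects who stop before 51 days without meeting either confirmed-rise item as non-virologic (premature discontinuation). List separately any who never fell below LLOQ, so that their resistance data are still shown.
3. State one outcome hierarchy, with SVR12 taking precedence in the failure-reason and virologic-failure tables (SVR4 for the lead-in). Keep this in the table rules, so that an on-treatment criterion is not redefined by a later result.
4. Have SAP 8.8 and 5.1 refer to this single definition.

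Deleting the item instead would be worse: a completer who stays quantifiable with no confirmed rise would then be neither an on-treatment failure nor a relapse.

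The cost is a few SAP sentences and the matching derivation lines. The downside is that a true non-responder who stops early is reported as non-virologic, which the separate listing makes visible. The stopping rule in Protocol 5.6.1 is not changed.

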#### **8.7.2.2. Post-Treatment Relapse**

Post-Treatment Relapse is defined as  $\text{HCV RNA} \geq \text{LLOQ}$  after treatment discontinuation in a subject who completed the treatment regimen (at least 51 days) and who had  $\text{HCV RNA} < \text{LLOQ}$  at the time of treatment discontinuation.

Note: Week 8 HCV RNA should be considered “on-treatment” in any subject who received 51 or more days of treatment.

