### **2.2. Secondary Objectives**

The secondary objectives of this study are:

- To evaluate the efficacy of BEM + RZR, as assessed by the proportion of subjects experiencing virologic failure (either on-treatment or post-treatment relapse [by 12 weeks post-treatment])
- To evaluate the efficacy of BEM + RZR as assessed by the proportion of subjects achieving SVR24

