### **5.6. Stopping Rules**

#### **5.6.1. Individual Virologic Stopping Rules**

Treatment will be discontinued in any subject with on-treatment virologic failure, defined as any one of the following:

- Confirmed  $1 \log_{10}$  increase in HCV RNA from post-baseline nadir
- Confirmed increase in HCV RNA  $\geq$  LLOQ in any subject who achieved HCV RNA  $<$  LLOQ

Confirmation should be performed as soon as possible after an initial HCV RNA value that may indicate virologic failure is reported.

After completion of study-related procedures in the current study, the investigator may offer an approved poststudy HCV treatment regimen consistent with local standard-of-care treatment guidelines to subjects who have on-treatment virologic failure or posttreatment virologic relapse. For those subjects who generally comply with the study protocol and experience lack of efficacy (failure to achieve SVR12 or SVR24) with the investigational regimen, the Sponsor may reimburse the investigator for the cost of a course of poststudy medication depending on local drug access and reimbursement policies.

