#### **8.4.2. Secondary Analyses**

Secondary analyses will include:

- The proportion of subjects in the PP population(s) experiencing virologic failure (on treatment or post-treatment relapse) by 12 weeks post treatment), estimated and presented with 95% CIs.
- The proportion of subjects in the PP population(s) achieving SVR24, analyzed using the same method as for SVR12.

Additional exploratory analyses will be performed and may include (but not be limited to) the following:

- The proportion of subjects in the PP population(s) achieving SVR12 by baseline NS5A and NS5B RAVs (yes/no), estimated and presented with 95% CIs.
- Emergence of NS5A and NS5B RAVs in the PP population(s), tabulated with proportions and CIs in subjects who experience virologic failure
- Assessment of response (e.g., SVR12 rates) by demographics and/or baseline characteristics including prior HCV treatment, baseline viral load, etc.

- HCV RNA change from baseline over time
- Exposure-response relationships

Additional details will be provided in the SAP.

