#### **6.5.3. Efficacy Evaluable Per-Protocol (EE-PP) Population**

The Efficacy Evaluable population will include subjects who:

1. Met all inclusion/exclusion criteria.
2. Did not receive concomitant medications that are prohibited due to their potential impact on HCV viral load or the pharmacokinetic concentration of either agent (BEM or RZR).
3. Have a collected or imputed (per Table 5) posttreatment viral load assessment at post treatment week 12, unless the subject discontinues early for virologic failure or AE, in which case the ET visit assessment may be used.
4. Has received at least one dose of study drug.

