### 8.8. Analysis of the Secondary Efficacy Endpoints

Secondary analysis will include:

- The proportion of subjects in the Efficacy Evaluable and Pill Compliant per-protocol populations (EE-PP and PC-PP) achieving sustained virologic response at 12 weeks post-treatment (SVR12). Table 5 will be used to derive SVR12 in the EE-PP and PC-PP populations.

- The proportion of subjects in the EE-PP, PC-PP and PK/PC-PP populations experiencing virologic failure (on treatment or post-treatment relapse), estimated and presented with 95% CIs using the Wilson score method.
- The proportion of subjects in the EE-PP , PC-PP and PK/PC-PP populations achieving SVR24, analyzed using the same method as for SVR12.

Virologic failure is defined as a confirmed 1 log10 increase in HCV RNA from post-baseline nadir, or confirmed increase in HCV RNA  $\geq$  LLOQ in any subject who achieved HCV RNA  $<$  LLOQ.

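### The SAP defines virologic failure in two conflicting ways, so some subjects who stop treatment early are scored oppositely under sections 8.7.2 and 8.8

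*SAP*

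**What the plan says.** **Protocol.** Section 2.2 makes the secondary endpoint "virologic failure (either on-treatment or post-treatment relapse [by 12 weeks post-treatment". Section 8.4.2 repeats the two components and the 12-week limit. Neither section sets a minimum exposure, and the protocol nowhere defines relapse. Section 5.6.1 does define on-treatment failure, as a treatment-stopping rule: "Treatment will be discontinued in any subject with on-treatment virologic failure, defined as any one of the following". It lists two criteria, a confirmed 1 log10 rise from the post-baseline low point and a confirmed return to the LLOQ or above. Non-response is not listed.

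**SAP 8.7.2.** There are two types of virologic failure.
- On-treatment failure (8.7.2.1) opens with "On-treatment virologic failure is defined as any of the following, while on-treatment". It keeps the protocol's two criteria and adds a third, never reaching RNA below the LLOQ, with no minimum exposure.
- Relapse (8.7.2.2) is RNA at or above the LLOQ after treatment "in a subject who completed the treatment regimen (at least 51 days", who was also below the LLOQ at discontinuation. Confirmation is not required.
- Premature discontinuation is named as a non-virologic reason for not achieving SVR.

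**SAP 8.8.** The endpoint is "The proportion of subjects in the EE-PP, PC-PP and PK/PC-PP populations experiencing virologic failure", with on-treatment failure and relapse as the components. The section then closes with its own definition: a confirmed 1 log10 rise from the low point, or a confirmed return to the LLOQ or above in anyone who had been below it. It states no 51-day condition, no on-treatment limit and no non-response criterion.

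**The concern.** Virologic failure is a named secondary endpoint. Two programmers following different sections of the same SAP could report different counts, and both would be following the plan.

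Under 8.7.2 taken alone, an early stopper is classified by the RNA value on the day the drug stopped. Below the LLOQ, a later recurrence belongs to neither failure category. At or above it, having never cleared, the subject is a virologic failure however short the exposure.

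The choice also reaches the resistance results. The emergent NS5A/NS5B variant summaries in SAP 8.9 are restricted to subjects with virologic failure, so the definition decides who enters those tables. It also affects how the reasons for not achieving SVR12 (Protocol 8.4.1) are labelled.

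**Working it through.** **1. The 51-day figure.** The SAP gives no derivation, but the figure matches its 90% compliance rule applied to 56 planned doses (SAP 4.2): 0.90 × 56 = 50.4, rounded up to 51. Check: 51/56 = 91.1% and 50/56 = 89.3%. It works as a definition of a completed course. The question is whether it belongs in the definition of failure.

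**2. The same subjects under both sections.**

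| Subject | SAP 8.7.2 | SAP 8.8 |
|---|---|---|
| A: stops on Day 35 below LLOQ; at or above LLOQ at follow-up | Not a failure (no on-treatment event; 35 < 51 days) | Failure, if confirmed |
| B: stops on Day 10, never below LLOQ, no confirmed 1 log10 rise | Failure (non-response) | Not a failure |
| C: completes treatment below LLOQ; one unconfirmed follow-up value at or above LLOQ | Failure (relapse) | Not a failure |

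The condition on B matters. Because 8.8 has no on-treatment limit, a confirmed 1 log10 rebound after stopping would make B a failure there too. Row C shows that the sections also differ on confirmation, even for completers.

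**3. Whether such subjects are in the analysis sets.** EE-PP sets no completion criterion. Its exposure condition is "Has received at least one dose of study drug", so A and B enter it with a qualifying RNA result. SAP 8.7.5 repeats all efficacy analyses in the safety population. PC-PP and PK/PC-PP admit A or B only if the stop was for a drug-related AE (or for virologic failure). Other early stops that miss the completion rule are excluded.

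**4. SVR12.** SAP Table 5 scores these subjects from the RNA result. Subject A with a Week 12 value at or above the LLOQ is an SVR12 failure under either definition.

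**5. Size.** The documents give no rate of early stopping or recurrence, so every count below is an assumption. With n = 280 (all enrolled subjects, the largest possible EE-PP), one subject is 1/280 = 0.36 points. Wilson 95% interval, z = 1.96: [p + z²/2n ± z√(p(1−p)/n + z²/4n²)] / (1 + z²/n).

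Assume 8 failures under 8.7.2: 8/280 = 2.9% (1.5 to 5.5). Adding early-stop recurrences only:
- 1 more: 9/280 = 3.2% (1.7 to 6.0)
- 3 more: 11/280 = 3.9% (2.2 to 6.9)
- 7 more: 15/280 = 5.4% (3.3 to 8.6)
- 14 more: 22/280 = 7.9% (5.2 to 11.6). This is an outer case in which all 280 − 266 = 14 subjects expected outside the per-protocol set stop early and recur.

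**6. Direction.** Step 5 ignores subjects like B, who move the other way. Let R be confirmed early-stop recurrences and N be early non-responders without a confirmed 1 log10 rise. Apart from differences in confirmation or non-response among completers, going from 8.7.2 to 8.8 changes the rate by (R − N)/n. Assume 10 early stops, with 70% (7) below the LLOQ at stopping and 3 not. The 70% is the Week 2 figure from AT-01B-002 (10 subjects, a different NS5A inhibitor; Protocol 1.1). If those 3 are among the 8 failures and R is 2 to 6:
- R = 2: 8 − 3 + 2 = 7, and 7/280 = 2.5%, a change of −1/280 = −0.36 points
- R = 6: 8 − 3 + 6 = 11, and 11/280 = 3.9%, a change of +3/280 = +1.07 points

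The sign depends on counts that the documents do not provide.

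**The case against.** A reader might infer that the protocol counts every relapse and that the SAP narrows it. The text does not support that. The protocol names relapse without defining it, and its section 8 leaves detailed methodology to the SAP. Supplying a definition is not a contradiction.

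A reader might also infer that early-stop recurrences are dropped from the secondary endpoint and that the reported rate is therefore too low. This does not hold either. Section 8.8 would count those recurrences if confirmed, and the non-response criterion in 8.7.2.1, which protocol 5.6.1 lacks, raises the count.

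The stronger defence is that 8.7.2 makes a deliberate choice. Premature discontinuation is labelled non-virologic, relapse is kept for completed courses, and the closing sentence of 8.8 merely echoes the on-treatment criteria of protocol 5.6.1. Separating recurrence after a short course from relapse after a full one is legitimate. Nor is the outcome hidden: SVR12 captures it, and resistance samples are taken at every visit, so only table membership is at issue.

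Much of this stands, but it does not remove the conflict. The 8.8 sentence says it defines virologic failure as a whole. Even if it were read as covering only the on-treatment part, it would still omit the non-response criterion in 8.7.2.1. A deliberate completers-only rule also does not explain why non-response counts after any exposure.

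**Conclusion.** The point holds as an internal conflict in the SAP. Sections 8.7.2 and 8.8 give different rules for one secondary endpoint and can score early stoppers in opposite ways. The protocol does not decide between them. The reach is mainly EE-PP and the safety population, plus drug-related-AE stoppers in PC-PP and PK/PC-PP and membership of the emergent-variant tables. The primary endpoint is not touched.

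Each reclassified subject is worth about 0.36 points. Under the assumed counts in which cases move both ways, the net shift runs from −0.36 to +1.07 points on a base of 2.9%. That is small beside the interval width but visible for a rate this low. No direction of bias can be claimed. The illustration rests on assumed numbers of failures, early stops and recurrences. The conflict itself rests only on the wording. It should be corrected before the analysis.

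**What to change.** Use one analysis definition of virologic failure in SAP 8.7.2 and 8.8, built on the protocol's two components and its 12-week limit, and state whether confirmation is required.

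- **Relapse:** count RNA at or above the LLOQ after treatment in a subject who was below it at the last on-treatment value. Report it on two lines, after at least 51 days and after early discontinuation.
- **Non-response:** apply it only to subjects with at least 51 days of treatment, and state that this criterion is an SAP addition. Report earlier stops at or above the LLOQ as premature discontinuation.
- **Resistance:** include early-stop recurrences in the emergent-variant tables.

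This concerns the analysis definition only and leaves the treatment-stopping rule in protocol 5.6.1 alone.

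The cost is SAP wording and one extra table row. The reported rate may move slightly in either direction. The completers-only relapse line remains available to anyone who prefers that reading.
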